7.3 Recruitment

7.3.1 Participant identification

Eligible babies are those in whom a positive culture has been obtained. Records will be identified by the local clinical team at each participating unit. The local team consisting of Neonatologists and research Nurses will then enter the relevant details onto an electronic data collection tool or web-based database, as part of their routine clinical duties. Data will be entered retrospectively on a regular basis either (weekly/monthly) depending on the unit activity and in compliance with the duties of the local team.

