5.2 Methods

The neonIN surveillance network captures data on episodes of invasive neonatal infection on a web-based database (www.neonin.org.uk). Over 30 UK neonatal units currently contribute to this database in real-time. An episode of neonatal infection is defined as a positive culture collected from a normally sterile site such as the blood, cerebrospinal fluid (CSF) or urine (via catheter or suprapubic aspirate) for which clinicians prescribed at least five days of appropriate antibiotics. Clinical, demographic and microbiological data (including antimicrobial susceptibilities) are collected using a standardised online questionnaire. Denominator data regarding the total number of live-births and neonatal-admissions are collected for each neonatal unit.

For the purpose of this study data will be entered onto an electronic data collection tool or web based database related to information on the baby's status at 28 days after the positive culture was obtained.

If the baby is alive, then this baby becomes eligible as a control. If the baby has died, then further details will be sought including the date of death and whether the infection was associated with the baby's death. Babies with positive cultures, but who have died before receiving 5 days of appropriate antimicrobial therapy (currently a component of the surveillance case definition), will also be captured prospectively.

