5.3 Data collection

Invasive infection episodes will be captured prospectively on a web-based infection surveillance database called neonIN (www.neonin.org.uk) which is coordinated by [name] at St George's University of London. The neonIN network currently includes 30 NNUs. For the purposes of this project all centres that wish to participate in neoAMRO will have access to the electronic data collection tool or web based database and will capture anonymised data regarding invasive episodes of infection.

For the purposes of the neoAMRO study, information on the baby's status at 28 days after the positive culture will be collected (alive / died / not known). If the baby is alive, then this baby becomes eligible as a control. However, if the baby has died, then further details will be sought including the date of death and whether the infection was believed to be associated with the baby's death. Babies with positive cultures but who have died before receiving 5 days of appropriate antimicrobial therapy (currently a component of the surveillance case definition), will also be captured prospectively.

Thus, the following data will be collected as part of the neoAMRO study:

- outcome at 28 days (alive / died / not known)
- date of death
- cause of death (if association with infection)
- antibiotics: name / start date / dose / frequency / stop date
- whether antibiotic regime was changed during therapy
- reason for change in antibiotic regime
- new antibiotics: name / start date / dose / frequency / stop date

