7 SAMPLE AND RECRUITMENT

7.1 Eligibility Criteria

There will be no exceptions (waivers) to eligibility criteria for data inclusion into the study.

The criteria have been carefully considered and are standards used to ensure the data can be appropriately selected, collected and appropriately analysed. It is therefore vital exceptions are not made to the following detailed selection criteria.

- Infants on participating NNUs who have an episode of infection with a positive culture.

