7.2 Sampling

7.2.1 Size of sample

Based on our previous data collection (see ref. 2), at the end of the enhanced study period we would expect to have data on up to 800 babies with invasive neonatal infections, approximately 50% will be due to coagulase negative staphylococci (CoNS), approximately 25% will be early onset sepsis and approximately 200 will be Gram-negative sepsis. Based on our recent data for case fatality rates (18% for Gram-negative bacteraemia, 8% for Group B streptococcus, 5% for staphylococcal aureus), we would expect around 50 deaths in this cohort.

All babies who have died within 28 days of a positive culture will then be compared with babies who have survived at 28 days across a range of relevant clinical and demographic factors. For all cases and for two controls per case (selected centrally, based on birth in same birthweight category and in same hospital), this will be performed through collection of anonymised data including birth gestation, birth weight and age at infection, antimicrobials administered for that infection episode (and if changed), relapses, length of stay and attributable mortality at 10 days using a standardised case report form. With approximately 50 cases of death and 100 controls, we anticipate that we will be able to explore the relationship between initial antimicrobial therapy and isolate susceptibility, with outcome, with great certainty. For example, with this sample size we can demonstrate a difference between susceptibility to empiric antibiotics of 80% among cases (or less) to 95% among controls, with 95% significance and 80% power; a difference that is clinically meaningful. A 10-day cut-off for attributable mortality will be used as early mortality is assumed to be more likely a direct consequence of infection than late mortality. Other risk factors for death will be assessed in univariate and multivariable logistic regression analyses.

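### The early-death route lifts the only treated-as-infection condition and replaces it with nothing, and section 7.2.1 then counts every 28-day death as a case

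*Protocol*

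**What the plan says.** Section 5.2 of the protocol defines an episode by two elements. The first is the site: "a positive culture collected from a normally sterile site such as the blood, cerebrospinal fluid (CSF) or urine" (urine by catheter or suprapubic aspirate). The second is treatment: "for which clinicians prescribed at least five days of appropriate antibiotics".

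Section 7.1 gives the formal criterion, "Infants on participating NNUs who have an episode of infection with a positive culture", and adds: "There will be no exceptions (waivers) to eligibility criteria for data inclusion into the study". Section 7.3.1, on how local teams find records, says only: "Eligible babies are those in whom a positive culture has been obtained".

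The Study Summary and sections 5.2 and 5.3 add a further group, to be captured prospectively: "Babies with positive cultures but who have died before receiving 5 days of appropriate antimicrobial therapy". The protocol itself notes that the five-day element is currently part of the surveillance case definition.

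For each death, section 5.3 has sites record the date and whether infection was believed to be associated with it. Section 7.2.1 defines the cases as all babies dying within 28 days of a positive culture and compares them with 28-day survivors. The secondary aim in the Study Summary describes the cases more narrowly, as babies who die from confirmed bacterial infections.

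**The concern.** Capturing early deaths is sensible, because a baby who dies on day 2 cannot complete five days of treatment. But the five-day element does two jobs. It sets a duration, and it is the only part of the entry definition showing that clinicians regarded the isolate as a real infection. The protocol has no entry criterion based on organism, repeat culture or clinical signs. Lifting the element for early deaths removes both jobs, and nothing is supplied for the second.

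The primary aims are to identify the infections leading to death and to describe the resistance profiles of the organisms responsible. Early deaths are the group that neoAMRO adds to the existing surveillance, and they are the group with no treated-as-infection test. In the case-control study the looser rule applies only to deaths, so cases and controls enter under different definitions.

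**Working it through.** **1. Does section 7.1 close the gap?** Two readings are possible.

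- If its episode of infection carries the whole of section 5.2, a baby who dies before the five-day element is met is ineligible and no waiver is allowed. This contradicts the Study Summary and sections 5.2 and 5.3, which admit such babies.
- If it does not carry the five-day element, an episode of infection has no definition for these babies beyond the positive culture and its site.

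On either reading, no section says what makes an early death an infection.

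**2. Who can enter?** Take two babies, each with one blood culture growing a skin commensal that clinicians judged to be a contaminant and did not treat.

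| | Section 5.2 five-day condition | Result |
|---|---|---|
| Survives to day 28 | applies, not met | not an episode, so not a control |
| Dies on day 2 of another cause | lifted, no substitute | can be captured, and is a case under section 7.2.1 |

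**3. Does a later step remove the second baby?**

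- The association of infection with death (section 5.3) is local opinion recorded after entry. Section 7.2.1 does not use it to select cases.
- The 10-day cut-off for attributable mortality (section 7.2.1) works the other way. It treats early mortality as more likely to be due to infection, and most early deaths would fall inside it.

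**4. The plan's own figures (section 7.2.1).**

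- Expected deaths: Gram-negative 200 × 18% = 36. Coagulase-negative staphylococci are about 50% of 800 = 400, which leaves 800 − 400 − 200 = 200 others. At the stated 5% to 8% these give 10 to 16 deaths. The total is 46 to 52, against the stated figure of around 50. This assumes that the three groups do not overlap. The projection is reached without any deaths with coagulase-negative staphylococci, for which no fatality rate is given, so early deaths with such an isolate may be cases that the plan did not count.
- Power for 80% v 95%, with 50 cases and 100 controls, two-sided 5%, groups treated as independent: pooled proportion (50 × 0.80 + 100 × 0.95)/150 = 0.90. Null standard error √[0.90 × 0.10 × (1/50 + 1/100)] = 0.0520. Alternative standard error √[0.80 × 0.20/50 + 0.95 × 0.05/100] = 0.0606. z = (0.15 − 1.96 × 0.0520)/0.0606 = 0.79, so power is 78.7%, close to the stated 80%.

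Both figures reproduce. Neither confirms nor refutes the point, which concerns definitions.

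**5. Can the bias be sized?** No. The documents give neither the number of early deaths, nor the share with a contaminant, nor the susceptibility of such isolates to the empiric regimen. The direction is also open. Controls are matched on birthweight category and hospital, not on organism, and about half the cohort is expected to have coagulase-negative staphylococci, so the controls will contain many such isolates too.

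**The case against.** The strongest reply is that the protocol should be read as a whole. Section 7.1 governs and has no waivers, section 7.3.1 is shorthand in a paragraph about who enters data, and section 5.3 confines capture to invasive episodes. That stands as far as the site is concerned. A reader might infer from section 7.3.1 that airway or surface cultures are admitted. The documents do not support this: no section drops the sterile-site condition, and the early-death sentence lifts only the five-day element. The reply does not cover the treated-as-infection element, for the reason in step 1 of the working.

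A second reply is that sites record whether infection was associated with death, so incidental growth can be kept off the list. This also stands in part. It would be too strong to say that contaminants will be listed as infections leading to death; they can be. The information is collected, but the protocol's stated case definition does not use it. Separate reporting lines may be left to an analysis plan that is not at hand. The entry rule and the case definition, however, are fixed in the protocol and do not agree.

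A reader might also want to put a number on a false difference in susceptibility by assuming a contaminant rate and a low susceptibility for contaminants. Any such figure rests wholly on assumed inputs. Low susceptibility in skin commensals would also be hard to square with the plan's 95% in controls, given how much of the cohort is expected to be coagulase-negative staphylococci.

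**Conclusion.** The point holds in a limited form. For early deaths the protocol removes its only treated-as-infection condition without a substitute, and this conflicts with section 7.1 read literally. Section 7.2.1 then counts all 28-day deaths as cases, although the Study Summary speaks of deaths from confirmed bacterial infections. Incidental or contaminant isolates can therefore enter among cases but not among controls.

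This rests on survivors being held to the full section 5.2 definition, which is how sections 5.2 and 7.1 read together. The size and direction of the effect are unknown. It is a cheap improvement, not a flaw that undermines the study.

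**What to change.** 1. In sections 7.1 and 7.3.1 and in each early-death sentence, state that the sterile-site condition of section 5.2 applies to every baby and that only the five-day duration is lifted for early deaths.
2. For early deaths, require evidence that the episode was regarded as infection: either the clinical-conditions item already collected (section 8.6), or antibiotics given for the suspected episode, whether or not they were active against the isolate. Do not require treatment directed at the isolate. That would drop babies who died on mismatched empiric therapy, which is the exposure under study.
3. Reconcile section 7.2.1 with the secondary aim in the Study Summary. Use the recorded association of infection with death for the tables of infections leading to death and in the case-control analysis, noting that it is local opinion.
4. Show early deaths with a skin commensal as sole isolate on a separate line, and repeat the main tables and the case-control comparison without them.

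The cost is protocol wording, a little more analysis and somewhat fewer cases in the repeat analysis. If, as an assumption, 10% to 20% of the 50 deaths were set aside, 50 × 0.90 = 45 to 50 × 0.80 = 40 cases would remain. With two controls each, the formula above gives power of 75% to 70% for 80% v 95%. Care is not affected.

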7.3.2 Consent

Informed consent will not be obtained in this study. There will be no change in the routine clinical care of any of the participants and as with the approved neonIN study no written consent will be sought from the individual participants.

7.3.3 Data collection tool

It is the Investigator's responsibility to ensure the accuracy of all data entered and recorded in the study database. The Staff Delegation of Responsibilities Log should identify all trial personnel responsible for data collection, entry, handling and managing the database.

7.3.4 Withdrawal

In the event where a subject's parents/carer refuse to be included in the study the local team should provide the subject study specific number (as recorded in their local records) to the study team at St George's University of London. The data controller will give the subject number to the data management team at St. George's University of London and request the subject to be removed from the database. Once this action is complete the data controller will inform the local team with a formal letter/email. The local team may communicate this action to the subject's parents/carer.

8 ETHICAL AND REGULATORY CONSIDERATIONS

8.1 Assessment and management of risk

This study is an observational study with no change to the clinical care of the study participants. There is therefore no risk to the care of the participant in this study.

Data collection forms in the study database will not bear the participant's name or other directly identifiable data. Only the local clinicians will have access to identifiable data for their patients. The risks associated with a breach of confidentiality are therefore extremely low.

COVID-19 Risk Assessment and Management Strategy

[This section applies to all research and should not be amended.](#)

All staff employed by SGUL and/or SGH NHS Foundation Trust are required to complete an ongoing COVID-19 risk assessment prior to undertaking any work on site, which includes research activity. This process is continuously monitored by the responsible line manager.

Participants (unaffected or affected) will not be recruited if they are deemed high risk or are in close contact with someone at risk. The Research Team will contact research participants ahead of scheduled study visits on-site to check for COVID-19 symptoms and the symptom check will be repeated when patients attend the hospital site for the study visit.

Participants will receive information regarding the extra precautions that will be taken in light of the COVID-19 pandemic in the Patient Information Sheet. This will detail steps that patients should take if they have concerns about exposure to COVID-19 through participating in the research, or believe that they are symptomatic or have been in close contact with another person believed to be symptomatic. The Patient Information Sheet will also have contact details for the Research Team for patients to get in touch if they have any concerns or queries about this.

All research personnel are expected to comply with the NHS Trust and University policies on COVID-19.

All patients attending the hospital site for research visits and/or routine clinical follow-up will be expected to abide by the NHS Trust and University policies on COVID-19 which include wearing suitable PPE (provided by the NHS Trust on arrival), adhering to the visitor policy on social distancing and following the one-way routing systems whilst on site.

The schedule of study assessments has been designed so that they align with the current routine clinical pathway for this patient population.

Therefore, research participants and site staff are not perceived to be at any additional risk of exposure to COVID-19 through participation in this research study.

8.2 Research Ethics Committee (REC) and other Regulatory review & reports

Before the start of the study, a favourable opinion will be sought from an appropriate REC for the study protocol and other relevant documents.

For HRA- NHS REC reviewed research

- Substantial amendments that require review by NHS REC will not be implemented until that review is in place and other mechanisms are in place to implement at site.
- It is the Chief Investigator's responsibility to produce the annual reports and submit the REC within 30 days of the anniversary date on which the favourable opinion was given, and annually until the study is declared ended.
- The Chief Investigator will notify the REC of the end of the study within one year after the end of the study.
- If the study is ended prematurely, the Chief Investigator will notify the REC, including the reasons for the premature termination.

Regulatory Review & Compliance

Before any site can enrol patients into the study, the Chief Investigator/Principal Investigator or designee will ensure that appropriate approvals from participating organisations are in place. Specific arrangements on how to gain approval from participating organisations are in place and comply with the relevant guidance.

Amendments

For any amendment to the study, the Chief Investigator or designee, in agreement with the sponsor will submit information to the appropriate body in order for them to issue approval for the amendment. The Chief Investigator or designee will work with sites (R&D departments at NHS sites as well as the study delivery team) so they can put the necessary arrangements in place to implement the amendment to confirm their support for the study as amended.

8.4 Patient & Public Involvement

The Patient Information Advisory Group was approached during the design of the neonIN database and their recommendations were considered.

The results will be published and disseminated at conferences, peer reviewed scientific journals and internal reports. Parents of infants can request to receive copies of any publications arising from the database.

8.5 Protocol compliance

Protocol deviations, non-compliances, or breaches are departures from the approved protocol.

All protocol deviations must be adequately documented on the relevant forms and reported to the Chief Investigator and Sponsor immediately.

Deviations from the protocol which are found to frequently recur are not acceptable, will require immediate action and could potentially be classified as a serious breach.

8.6 Data protection and patient confidentiality

All data should be handled in accordance with the Data Protection Act 2018 (UK implementation of the EU General Data Protection Regulation (GDPR)).

The participant's trial Identification Number (ID) only, will be used for identification. The Subject ID log can be used to cross reference participant's identifiable information and will be stored securely at participating sites.

1. Describe the nature of the processing:

A member of the neonatal team at each centre will be responsible for data collection and data input. As infection cases arise, they will be entered onto an electronic data collection tool or web based database. The central database will be anonymised with subjects identified only by neonIN study number, SEND/BADGER number and date of birth. Once age at infection has been calculated the DOB will be removed from the database. Each participating unit will hold its own secure database in order to link the infants' identifying data with study numbers. All data will be stored in compliance with the Data Protection Act.

2. Describe the scope of the processing:

Routine data collected: contributing hospital, DOB (for calculation of age at infection), gender, birth weight, gestation, ward type, date blood culture taken, pathogens isolates, whether the baby received

antibiotics 48 hrs before the culture was taken, whether the mother received antibiotics in the week before delivery, presence of intravenous or arterial lines catheters at time the culture sample was taken, clinical conditions associated with the infection, results of positive cultures including antibiogram, country of the participating unit, date of admission to the neonatal unit, number allocated to the baby on the SEND/Badger database, denominator data from each participating unit to demonstrate the unit activity (number of live births, number of admissions, patient days in NNU, central line days).

The following data to be collected in addition to the neonIN data, as part of the neoAMRO study : outcome at 28 days (alive / died / not known), date of death, cause of death (if association with infection), antibiotics: name / start date / dose / frequency / stop date, whether antibiotic regime was changed during therapy, reason for change in antibiotic regime, new antibiotics: name / start date / dose / frequency / stop date.

The data will be kept for 5 years post study termination/end.

8.7 Indemnity

St George's University of London holds insurance to cover participants for injury caused by their participation in the clinical trial. Participants may be able to claim compensation if they can prove that St George's has been negligent. This includes negligence in the writing of the protocol, or selection of trial resources.

Where the Trial is conducted in a hospital, the hospital has a duty of care to participants. St George's University of London will not accept liability for any breach in the hospital's duty of care, or any negligence on the part of hospital employees.

If a participant indicates that they wish to make a claim for compensation, this needs to be brought to the attention of St George's University of London immediately.

Failure to alert St George's University of London without delay and to comply with requests for information by the sponsor or any designated Agents may lead to a lack of insurance cover for the incident.

